1. OBJECTIVES

1.1 Study Design

This is a prospective, open label, single center study designed to evaluate the activity and tolerability of apixaban for the treatment of hospitalized patients with a confirmed diagnosis of isolated heparin induced thrombocytopenia or heparin induced thrombocytopenia with thrombosis (HIT and HITT, respectively).

Hospitalized patients who have a confirmed diagnosis or highly suspicious symptoms of HIT will be treated with therapeutic dosing as approved by FDA of apixaban. Study length will be 30 days from the time of initiation of apixaban in patients with isolated HIT, defined as HIT without thrombosis, and 3 months for patients with HITT (heparin induced thrombocytopenia with thrombosis). Treatment will continue until completion of the study, unacceptable toxicity or at the discretion of the investigator and patient. Markers of disease activity (e.g. thrombocytopenia, TEC, death) will be assessed at baseline, daily during the initial treatment period with apixaban while patients are hospitalized and at 30-day follow-up for isolated HIT and 3 month follow up for HITT.

1.2 Primary Objectives

To evaluate the activity of apixaban as monotherapy in patients with isolated heparin induced thrombocytopenia and HITT, as defined by the incidence of new symptomatic thromboembolic complications (TEC) within 30 days of the time of initiation of apixaban.

1.3 Secondary Objectives

To evaluate the safety and efficacy of apixaban in the treatment of HIT and HITT within 30 days of enrollment, as defined by:

- the composite incidence of all-cause death, amputation and new TEC
- individual components of the composite endpoint
- composite incidence of new TEC and major bleeding
- the incidence of major bleeding
- the time to platelet recovery * as a surrogate index of the activity of apixaban.

*Time to platelet recovery is defined in section 11.1.4

2. BACKGROUND

2.1 Study Disease(s)

Heparin-induced thrombocytopenia type-II (HIT) is a common and frequently severe syndrome characterized by thrombocytopenia and a prothrombotic state following exposure to unfractionated heparin (UFH) or low molecular weight heparin (LMWH).¹ The incidence of HIT ranges from 0.3-5.0% depending on the patient population and the type and route of heparin used.¹⁻⁴ It is an antibody-mediated reaction caused by the binding of platelet-activating IgG antibodies to platelet factor 4–heparin complexes on the surface of platelets, and it typically manifests 4-10 days after the initiation of heparin therapy, but it can occur as quickly as a few hours in patients who have received heparin within the previous 100 days.⁵⁻⁷

Patients diagnosed with HIT are at high risk for life-threatening thrombotic sequelae, up to 55% if untreated.⁴ Recognition of the diagnosis, discontinuation of heparin therapy and immediate intervention with a non-heparin anticoagulant are critical for preventing thromboembolic complications (TEC) and restoring a normal platelet count. When HIT is accompanied by thrombosis, it is termed HITT; when it is not accompanied by thrombosis, it is termed isolated HIT. Without evidence of TEC at the time of recognition, patients are regarded as having “isolated” HIT. Such patients are recognized as having HIT due to a characteristic decline in the platelet count following the administration of heparin. This decrease in the platelet count may occur immediately, as with a history of recent prior exposure (and thus antibodies are already present when heparin is recommenced), or after a delay of approximately five to ten days in patients without antibodies at baseline who are newly or repeatedly exposed to heparin. The diagnosis may be confirmed objectively by one of a number of available laboratory tests including the serotonin-release assay, the platelet aggregation assay, or the heparin-platelet factor 4 (PF4) enzyme-linked immunoassay (EIA).^{5,8,9} While diagnostic specificity can be augmented by the use of functional studies, the heparin-PF4 EIA is the present, accepted standard for confirming the diagnosis of HIT in the United States.¹⁰

Standard therapy in the United States for HIT(T) involves immediate administration of the direct thrombin inhibitor (DTI), argatroban.¹⁰ Based on a significant reduction of a composite endpoint of thromboembolic events, limb amputation and death in patients with HIT(T) compared to a historical control, argatroban was approved by the FDA for use in patients with HIT or HIT with thrombosis (HITT). A review of the two prospective clinical studies reporting argatroban administration in the acute treatment of isolated HIT reveals an incidence of TEC ranging from 6-8% among treated patients.^{11,12} However, two recently published studies report much higher TEC rates. A case series aimed at identifying risk factors associated with the development of TEC report a rate of 25%.¹³ A “real world” analysis of 442 patients with a positive PF4 antibody test and heparin exposure had a composite endpoint of death, limb amputation or new thrombosis as the primary outcome. This composite endpoint occurred in 48% of the HITT patients and in 36% of the isolated HIT patients, of which 61% and 38% were treated with non-heparin anticoagulation, respectively.¹⁴ These recent studies more accurately reflect current trends.

In the absence of thromboembolic disease, the duration of treatment is debated. Based on a

retrospective cohort analysis documenting a high (52.8%) VTE risk at 30 days following diagnosis, a minimum of four weeks of therapeutic anticoagulation after normalization of the platelet count is appropriate.⁴ Early transition to warfarin is contraindicated due to the increased risk of microvascular thrombotic complications including skin necrosis and venous limb gangrene while patients are thrombocytopenic.^{15,16} Therefore practice standards require therapeutic anticoagulation with a DTI until the platelet count has demonstrated recovery, followed by a period of 5 or more days of continuous intravenous therapy with a DTI while transitioning to oral warfarin.^{10,17}

2.2 IND Agent: Apixaban

Apixaban is an ideal alternative for the treatment of HIT or HITT because it is administered orally with fixed dosing, requires no routine coagulation monitoring and is FDA approved in the treatment of venous and arterial thromboembolism in other settings.^{18,19} It inhibits free and clot-bound FXa resulting in decreased thrombin generation and thrombus formation and is structurally unrelated to heparin. An *in vitro* study demonstrated that apixaban does not aggregate or activate platelets in the presence of HIT antibodies.²⁰ Furthermore, a recent case series of 22 HIT patients showed that treatment with a short course of argatroban followed by a new oral anticoagulant (NOAC) was safe and effective in normalization of platelets and prevention of thrombosis.²¹ Moreover, there is one case report revealing that treatment with apixaban as monotherapy for the management of HIT was successful in terms of platelet recovery and lack of adverse events.²² Thus, apixaban is attractive alternative to DTIs for the treatment of HIT and HITT.

2.3 Rationale

Heparin-induced thrombocytopenia type-II (HIT) is a common and often severe complication of heparin therapy. Although the central feature of HIT is thrombocytopenia, the more worrisome complication is the development of arterial or venous thrombosis often referred to as heparin-induced thrombocytopenia-thrombosis syndrome (HITT). The exact incidence of HIT associated thrombosis is not well established but studies demonstrate a range from 10% to as high as 55%.⁴ In addition, the mortality associated with this complication has been reported to be as high as 20%.^{4,9,10} Given this high rate of mortality and the awareness of prolonged thrombin generation even after heparin is discontinued, establishing the diagnosis, discontinuing heparin therapy and immediately intervening with a non-heparin anticoagulant are critical for preventing thromboembolic complications (TEC).⁸

Presently there is only one available alternative (Argatroban) to heparin that is FDA approved for HIT or HITT in this country that can be used as a bridge to coumadin.^{9,10} Argatroban is a direct thrombin inhibitor (DTI), administered intravenously, requires continuous laboratory monitoring, can cause excessive bleeding and is extremely costly. Non FDA agents that are often used are fondaparinux or bivalirudin, the former requires an injection and the later is similar to Argatroban (and is approved for HIT in patients undergoing PCI). Practice standards require therapeutic anticoagulation with a DTI until platelet count recovery, followed by 5 or more days of overlap while transitioning to oral warfarin with goal INR 2-3 for 1 month for patients with HIT and 3 months for patients with HITT.^{8,11} Thus, anticoagulating patients with HIT has

become a huge expense and burden on our health care system.

There are several potential benefits to apixaban therapy compared to treatment with the direct thrombin inhibitor, argatroban. Argatroban requires continuous intravenous administration, typically requiring protracted inpatient hospitalization for at least six to thirteen days based on the published mean duration of therapy with direct thrombin inhibitors reported in clinical trials. The oral route of apixaban allows for the potential outpatient treatment of HIT in selected patients, akin to the widespread use of subcutaneous danaparoid sodium in HIT prior to its withdrawal from the United States market. Whereas direct thrombin inhibitors are unfamiliar to many practitioners and require careful titration of coagulation parameters, apixaban has a reliable pharmacokinetic profile and does not require plasma monitoring. Furthermore, conversion to oral warfarin from a DTI, which is the current standard of care for HIT, is complicated by cessation of DTI anticoagulation while assessment of therapeutic warfarin dosing is determined. In addition to the requirement of inpatient hospitalization, direct thrombin inhibitors are costly medications compared to the cost of apixaban. Thus, apixaban appears attractive as an alternative to direct thrombin inhibitor therapy in the treatment of HIT.

Another desirable features of apixaban is the benefit of immediate anticoagulation in these highly prothrombotic and hypercoagulable patients. The incidence of TEC in HIT is greatest in the earliest phase of disease.⁴ Immediate alternative anticoagulation is, therefore, indicated in all patients where HIT is suspected. However, therapeutic anticoagulation with a DTI may be difficult to achieve initially, in routine clinical practice. In a prospective trial of argatroban in the treatment of HIT, only 83% of patients ultimately achieved therapeutic anticoagulation.¹¹ Pharmacokinetic studies of apixaban suggest that peak plasma concentration is reached within 3 hours of administration, with a highly reproducible pharmacokinetic profile.²³ Therefore, patients treated with apixaban are more likely to be effectively anticoagulated earlier in the course of the most hazardous phase of their disease.

The ideal study would be a randomized controlled trial comparing apixaban with the FDA approved treatment for HIT, argatroban. However, this is impractical due to cost and time constraints as it would require a large sample size and take years to accrue. Although this is only a single site study, accruing to this study should not be difficult. HIT is a frequent diagnosis at Massachusetts General Hospital (MGH). There is an average of five positive HIT tests each week and over half of those are from patients who are in the hospital. Over a 5 month period, from Oct 2015 to March 2016, there were 52 patients at MGH who received an intravenous direct thrombin inhibitor (DTI) - either argatroban or bivalirudin. This number is likely an underestimate of the number of HIT patients requiring treatment as it does not include those patients who were treated with fondaparinux alone. Moreover, it is important to note that at MGH, patients diagnosed with HIT can only receive a DTI if approved by the hematology service. Therefore, the principle investigator will be alerted to every HIT patient who potentially requires a DTI and if eligible, can offer the trial instead.

3 PARTICIPANT SELECTION

The potential participants in this study are hospitalized patients who receive heparin or low molecular weight therapy for various indications. When a clinical diagnosis or high suspicion for HIT is apparent, heparin therapy should be discontinued. Before a patient starts apixaban, they will be screened to determine their eligibility to participate in the study based on the following inclusion/exclusion criteria:

3.1 Eligibility Criteria

3.1.1 Hospitalized patients at MGH and participating Dana Farber/Harvard Cancer Center (DF/HCC) sites.

3.1.2 Patient must have a 4 T score of ≥ 5 as calculated by the following criteria:

- **Thrombocytopenia**
 - Platelet count fall >50 percent and nadir $\geq 20,000$ /microL – 2 points
 - Platelet count fall 30 to 50 percent or nadir 10 to 19,000/microL – 1 points
 - Platelet count fall <30 percent or nadir $<10,000$ /microL – 0 points
- **Timing of platelet count fall**
 - Clear onset between days 5 and 10 or platelet count fall at ≤ 1 day if prior heparin exposure within the last 30 days – 2 points
 - Consistent with fall at 5 to 10 days but unclear (eg, missing platelet counts), onset after day 10, or fall ≤ 1 day with prior heparin exposure within 30 to 100 days – 1 point
 - Platelet count fall at <4 days without recent exposure – 0 points
- **Thrombosis or other sequelae**
 - Confirmed new thrombosis, skin necrosis, or acute systemic reaction after intravenous unfractionated heparin bolus – 2 points
 - Progressive or recurrent thrombosis, non-necrotizing (erythematous) skin lesions, or suspected thrombosis that has not been proven – 1 point
 - None – 0 points
- **Other causes for thrombocytopenia**
 - None apparent – 2 points
 - Possible – 1 point
 - Definite – 0 points

3.1.3 Patient must meet one of the following:

- Have a confirmed diagnosis of HIT by Heparin-PF4 EIA or other accepted confirmatory test (serotonin-release assay, platelet aggregation assay).
- Have a high clinical suspicion of HIT (either Heparin-PF4 result is pending, or Heparin-PF4 result is negative or not obtained but a confirmatory test is pending)

Testing for HIT at MGH and participating DF/HCC sites is extremely reliable. MGH and participating DF/HCC sites currently use an extensively validated PF4-H IgG-based ELISA for HIT which has 94% specificity with a negative predictive value of 99.7% and a sensitivity that is close to 95%.

- 3.1.4 Patients can be treated with a non-heparin anticoagulant (such as argatroban, bivalirudin, or fondaparinux) for up to 7 days prior to enrollment.
- 3.1.5 Age 18 years or older.
- 3.1.6 ECOG performance status ≤ 2
- 3.1.7 Participants must have organ and marrow function as defined below:
- absolute neutrophil count $\geq 1,500/\text{mcL}$
 - AST(SGOT) and ALT(SGPT) $\leq 2.5 \times$ institutional upper limit of normal
 - creatinine clearance $\geq 25 \text{ mL/min}$ as was used in the AMPLIFY trial¹⁶
(Per Cockcroft-Gault formula)
- 3.1.8 The effects of apixaban on the developing human fetus are unknown. For this reason, women of child-bearing potential and men must agree to use adequate contraception (hormonal or barrier method of birth control; abstinence) prior to study entry and for the duration of study participation. Should a woman become pregnant or suspect she is pregnant while she or her partner is participating in this study, she should inform her treating physician immediately. Men treated or enrolled on this protocol must also agree to use adequate contraception prior to the study, for the duration of study participation, and 4 months after completion of apixaban administration.
- 3.1.9 Ability to understand and the willingness to sign a written informed consent document.

3.2 Exclusion Criteria

- 3.2.1 Patient requires anticoagulation for a mechanical heart valve.
- 3.2.2 Patient requires:
- dual antiplatelet therapy,
 - treatment with aspirin at a dose of more than 162 mg daily
- 3.2.3 Patient has signs of active or ongoing clinically significant hemorrhage.
- 3.2.4 Patient has hereditary or acquired coagulopathy or bleeding disorder.
- 3.2.5 Patient has a contraindication to apixaban.

- 3.2.6 Participants receiving any medications or substances that are inhibitors or inducers of cytochrome P-450 3A4 or p-glycoprotein are ineligible. Because the lists of these agents are constantly changing, it is important to regularly consult a frequently-updated list such as <http://medicine.iupui.edu/clinpharm/ddis/table.aspx>; medical reference texts such as the Physicians' Desk Reference may also provide this information. As part of the enrollment/informed consent procedures, the patient will be counseled on the risk of interactions with other agents, and what to do if new medications need to be prescribed or if the patient is considering a new over-the-counter medicine or herbal product.
- 3.2.7 Patient has severe renal insufficiency (CrCl <25 ml/min—as used in the AMPLIFY trial)¹⁶
- 3.2.8 Patient has hepatic disease (including Child-Pugh B and C) associated with coagulopathy or clinically relevant bleeding risk. See appendix F for definition
- 3.2.9 Recent (previous seven days), or complicated lumbar puncture or epidural catheter placement or removal.
- 3.2.10 Patient has high potential need to undergo a surgical or major invasive procedure in the near future.
- 3.2.11 Patient has a history of uncorrected cerebral aneurysm, intracranial tumor or hemorrhagic cerebrovascular accident.
- 3.2.12 Patient refuses to receive transfused blood products should this intervention become clinically indicated.
- 3.2.13 Patient is taking or has been taking an investigational drug within the previous 30 days prior to enrollment.
- 3.2.14 In the judgment of the investigator, any disease or circumstance that would interfere with the objectives of the study, that places the patient at undue, increased risk by enrolling in the study, or which limits the ability either to provide signed informed consent or comply with the trial protocol.
- 3.2.15 Participants with known brain metastases should be excluded from this clinical trial because of their poor prognosis and because they often develop progressive neurologic dysfunction that would confound the evaluation of neurologic and other adverse events.
- 3.2.16 History of allergic reactions attributed to compounds of similar chemical or biologic composition to apixaban.

- 3.2.17 Uncontrolled intercurrent illness including, but not limited to, ongoing or active infection, symptomatic congestive heart failure, unstable angina pectoris, cardiac arrhythmia, or psychiatric illness/social situations that would limit compliance with study requirements.
- 3.2.18 Pregnant women are excluded from this study because apixaban is a Class B agent with unknown potential for teratogenic or abortifacient effects. It is unknown whether apixaban or its metabolites are excreted in human milk. Because there is an unknown but potential risk for adverse events in nursing infants secondary to treatment of the mother with apixaban, breastfeeding should be discontinued if the mother is treated with apixaban.
- 3.2.19 Prior treatment with a non-heparin anticoagulant while awaiting study enrollment is not an exclusion.

3.3 Inclusion of Women and Minorities

Both men and women of all races and ethnic groups are eligible for this trial.

4 REGISTRATION PROCEDURES

4.1 General Guidelines for DF/HCC Institutions

Institutions will register eligible participants in the Clinical Trials Management System (CTMS) OnCore. Registrations must occur prior to the initiation of any protocol-specific therapy or intervention. Any participant not registered to the protocol before protocol-specific therapy or intervention begins will be considered ineligible and registration will be denied.

An investigator will confirm eligibility criteria and a member of the study team will complete the protocol-specific eligibility checklist.

Following registration, participants may begin protocol-specific therapy and/or intervention. Issues that would cause treatment delays should be discussed with the Overall Principal Investigator (PI). If the subject does not receive protocol therapy following registration, the subject must be taken off-study in the CTMS (OnCore) with an appropriate date and reason entered.

4.2 Registration Process for DF/HCC Institutions

DF/HCC Standard Operating Procedure for Human Subject Research Titled *Subject Protocol Registration* (SOP #: REGIST-101) must be followed.

5 TREATMENT AND/OR IMAGING PLAN

5.1 Treatment Regimen

Patients eligible for the study will receive the standard of care and FDA approved dosing of apixaban. Platelet count recovery in patients with HIT is typically 5-7 days. Warkentin demonstrated that patients with isolated HIT (HIT without thrombosis) have an increased risk of thrombosis for up to 30 days after diagnosis.⁴ Therefore, for patients with isolated HIT (HIT without thrombosis), patients will receive apixaban, 10 mg twice a day for 7 days followed by 5 mg twice a day for 23 days, for a total of 30 days of apixaban dosing. For patients with HITT, patients will receive apixaban, 10 mg twice a day for 7 days followed by 5 mg twice a day for 83 days, for a total of 90 days of apixaban dosing, which are the current CHEST guidelines for duration of treatment for patients with provoked VTE.²⁴ The proposed apixaban dosing regimen is taken from the current FDA approved dosing schedule for the treatment of venous thromboembolism [VTE] with apixaban which is 10 mg twice daily for 7 days followed by 5 mg twice daily thereafter.

Treatment will initially be administered on an inpatient basis but once patient is medically cleared to be discharged, the remaining treatment will be administered on an outpatient basis. Reported adverse events and potential risks are described in Section 7. Appropriate dose modifications are described in Section 6. No investigational or commercial agents or therapies other than those described below may be administered with the intent to treat the participant.

Regimen Description					
Agent	Premedications; Precautions	Dose	Route	Schedule*	Length of treatment
Apixaban	No premedications required	10 mg twice a day	Oral	For the first 7 days**	1 month (30 days) total for HIT patients and 3 months (90 days) total for HITT patients
Apixaban	No premedications required	5 mg twice a day	Oral	To start this dose after patient completes the first 7 days with the 10 mg twice a day dose.**	

* This is the FDA approved dose for apixaban for prevention and treatment of venous thromboembolism.
 
** Patients will not start the 5 mg dose prior to 7 days as this is the FDA approved dosing structure.
					

NOTE: Patients will be requested to maintain a medication diary of each dose of medication. The medication diary will be returned to clinic staff at the end of the study (one month for HIT patients and 3 months for HITT patients).

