- Blood coagulation profile: Activated partial thromboplastin time (aPTT), prothrombin time/international normalized ratio (PT/INR).
- Serum Chemistries: creatinine, BUN, Na, K, CO₂ and glucose.
- Hepatic Profile: total bilirubin, AST, ALT.

5.3.2 **Imaging (Day -7 to Day +3)**

- As part of standard of care, all patients with confirmed HIT or high suspicion of HIT undergo bilateral lower extremity non invasive testing to rule out deep vein thrombosis. LENI is not required if the patient is diagnosed with a Pulmonary Embolism.
- This can occur anytime from Day -7 to Day +3. Only one test is required.

5.3.3 **Initiation of Therapy: Day 1**

Once the patient has been consented and is determined to meet inclusion/exclusion criteria as described above in Section 3.1 and 3.2, the following study procedures will be performed. These assessments do not need to be repeated if Screening was conducted on D1.

- Physical Exam
- Clinical Assessment for signs and symptoms of TEC and any significant findings
- Vital signs
- Weight
- ECOG
- Laboratory tests:
 - CBC: hemoglobin, hematocrit, WBC with differential, and platelet count
 - Chemistries: creatinine, BUN, Na, K, CO₂ and glucose
 - Hepatic panel: total bilirubin, AST, ALT
 - Coagulation profile: aPTT, PT/INR
- Record Concomitant Medications
- Assess and Record Adverse Events
- Initiation of Therapy: dispense study medication and diary
 - Administer study medication: Apixaban
 - Initiate daily oral therapy at 10 mg twice daily for 7 days followed by 5 mg twice daily thereafter.

5.3.4 **Hospital Course: Day 2 - Day of Discharge:**

The following procedures will be done on a daily basis until discharge from the hospital:

- Clinical Assessment for signs and symptoms of thromboembolic complications and any significant findings.
- Vital signs
- Laboratory Tests:
 - CBC: hemoglobin, hematocrit, WBC with differential, and platelet count
 - Chemistry Panel: creatinine, BUN, Na, K, CO2 and glucose
- Assess and record Adverse Events
- Record Concomitant Medications
- Record all doses of administered Apixaban (from the day it was initiated).

Before discharge, ensure enough study medication is dispensed to last at least until the 30 Day Follow Up visit (for HIT) or the 90 Day Follow Up visit (for HITT).

5.3.5 **Follow-up: Day 30 (+/- 5 days)**

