The patient will be assessed on Day 30 (\pm 5 days) from initiation of therapy, preferably in clinic. If clinic follow up is feasible, all of the following data must be recorded. If patient is unable to come to clinic (ie due to living in another city or unable to travel), day 30 follow up can be completed by telephone interview and the labs, exam and vitals will not be recorded.

The following data must be recorded:

- Summary of patient's clinical course
- Any adverse events that occurred between Day of Discharge through Day 30 including signs and symptoms of TEC.
- CBC, chemistries, coagulation profile*
- Physical exam and vital signs*
- Concomitant Medications
- For patients discharged on apixaban:
 - Retrieve study medication and diary
 - Record the stop date of discontinuation of apixaban.

**unable to obtain if follow up is telephone interview*

5.3.6 **Follow-up for patients with HITT: Day 90 (+/- 5 days)**

The patient will be assessed on Day 90 (± 5 days), from initiation of therapy, preferably in clinic. If clinic follow up is feasible, all of the following data must be recorded. If patient is unable to come to clinic (ie due to living in another city or unable to travel), day 90 follow up can be completed by telephone interview and the labs, exam and vitals will not be recorded.

The following data must be recorded:

- Summary of patient's clinical course
- Any adverse events that occurred between Day of Discharge through Day 90 including signs and symptoms of TEC.
- CBC, chemistries, coagulation profile*
- Physical exam and vital signs*
- Concomitant Medications
- For patients discharged on apixaban:
 - Retrieve study medication and diary
 - Record the stop date of discontinuation of apixaban.

**unable to obtain if follow up is telephone interview*

5.3.7 **Follow-up 30 days after last dose of therapy (+/- 5 days)**

The patient will be assessed on 30 days (± 5 days), after last dose of therapy. If clinic follow up is feasible, all of the following data must be recorded. If patient is unable to come to clinic (ie due to living in another city or unable to travel), this follow up can be completed by telephone interview and the labs, exam and vitals will not be recorded.

The following data must be recorded:

- Summary of patient's clinical course
- Any adverse events through 30 days after the last dose of therapy including signs and symptoms of TEC.
- CBC, chemistries*
- Physical exam and vital signs*
- Concomitant Medications

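### The Day 30 visit may fall on Day 25, and its instructions have staff take back study drug without checking that the 30-day (isolated HIT) or 90-day (HITT) course is finished

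*Combined protocol and SAP*

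**What the plan says.** **Prescribed course.** Section 5.1 starts isolated HIT with one week at 10 mg twice daily; the remainder reads "followed by 5 mg twice a day for 23 days, for a total of 30 days of apixaban dosing". It explains the length by noting that these patients "have an increased risk of thrombosis for up to 30 days after diagnosis". HITT patients get 7 days at 10 mg and 83 days at 5 mg, 90 days in all. Section 5.7 repeats one month and three months and lists the reasons for stopping sooner; an early visit is not among them.

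**Visit steps.** Section 5.3.5 places the Day 30 visit within 5 days either side, and the note in 5.10 counts days from the start of treatment. At that visit the step headed "For patients discharged on apixaban" is "Retrieve study medication and diary", followed by recording the date apixaban was stopped. The section applies to all patients. Section 5.3.6 adds a Day 90 visit (also within 5 days either side) for HITT, with the same retrieval step.

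**Supply and diary.** Section 5.3.4 tells staff to "ensure enough study medication is dispensed to last at least until the 30 Day Follow Up visit (for HIT"), and sets the Day 90 visit as the corresponding point for HITT. Footnote 13 of the study calendar says the same without the words that make it a minimum. On the diary, the note in 5.1 says that it "will be returned to clinic staff at the end of the study (one month for HIT patients and 3 months for HITT patients").

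**Calendar.** Section 10 marks drug and diary return at both the 30-day and 90-day visits. It labels the 90-day column as being for isolated HIT, although 5.3.6 assigns that visit to HITT.

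**The concern.** The course length and the visit checklist give staff two different instructions. A coordinator who sees an isolated-HIT patient in clinic on Day 25 and works through 5.3.5 would take the tablets and enter a stop date, although five days of treatment remain. No text says that a patient who has not finished keeps the drug. The calendar does not resolve the matter, because it marks return at both visits and puts the wrong group over the Day 90 column.

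A stop on Day 25 falls inside the 30-day period, counted from the first apixaban dose, over which the primary endpoint is assessed (Sections 1.2 and 13.1). A course shortened by the schedule would then be part of the treatment being evaluated, without anyone having decided to shorten it.

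There is a smaller point about follow-up. The visit is meant to capture "Any adverse events that occurred between Day of Discharge through Day 30 including signs and symptoms of TEC", which a visit on Days 25 to 29 cannot do by itself.

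**Working it through.** **Inputs**
- Dosing: 7 + 23 days (isolated HIT) and 7 + 83 days (HITT), twice daily, from 5.1.
- Windows: Day 30 and Day 90, each plus or minus 5 days, from 5.3.5 and 5.3.6.
- Tablet strength: 5 mg, from 5.4.2, so a 10 mg dose is two tablets.
- Post-treatment contact: 30 days after the last dose, plus or minus 5, from 5.3.7.

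**The plan's own totals.** 7 + 23 = 30 days and 7 + 83 = 90 days. Both reproduce.

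**Planned doses**
- Isolated HIT: 7 x 2 + 23 x 2 = 14 + 46 = 60.
- HITT: 7 x 2 + 83 x 2 = 14 + 166 = 180.

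**Earliest permitted visit**
- Isolated HIT: 30 - 5 = Day 25. If both doses are taken on the visit day, Days 26 to 30 are lost: 5 days x 2 = 10 doses. 5/30 = 10/60 = 17%. All ten are 5 mg doses, so 10/46 = 22% of that phase.
- If neither dose is taken on the visit day, one more day is lost, making 6 days.
- HITT: 90 - 5 = Day 85. The loss is 5 days, or 10 of 180 doses: 5/90 = 6%.

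**How much of the window is affected.** Days 25 to 35 are 11 days, of which Days 25 to 29 (5 days) precede Day 30. The documents do not say how visits will be distributed, so no average loss can be derived. The range for isolated HIT is 0 to 5 days, and it is 0 for any visit from Day 30 onward (both doses on the visit day counted as taken, as above).

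**Supply in 5 mg tablets, counted from Day 1 and including inpatient doses**
- Full isolated-HIT course: 7 x 2 x 2 + 23 x 2 = 28 + 46 = 74.
- Supply only to a Day 25 visit: 28 + (25 - 7) x 2 = 28 + 36 = 64, ten short.
- Full HITT course: 28 + 83 x 2 = 28 + 166 = 194.

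**Next contact after an early stop.** With a last dose on Day 25, the 5.3.7 contact falls at 25 + 30 plus or minus 5, that is Days 50 to 60. It asks about events through 30 days after the last dose, so it covers Days 26 to 30 for any patient who is reached.

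**The case against.** The strongest reply is that the regimen itself is consistent: 5.1 and 5.7 fix the duration, 5.7 lists the grounds for stopping, and a visit early in the window is not one of them. A stop date can be recorded only for someone who has stopped, so a sensible coordinator would leave the drug with an unfinished patient. Telephone visits collect nothing. The minimum wording in 5.3.4 allows a full 30-day supply. All of this stands, and it means that nothing here shows an intention to stop early. It does not remove the conflict, because the visit step is unconditional and no sentence tells staff to do otherwise.

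Four stronger readings are tempting, and the documents do not support them.

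- **HITT patients will lose most of their treatment at Day 30.** Retrieval on Days 25 to 35 without re-issue would remove 55 to 65 of 90 days. But HITT supply is set to the Day 90 visit, their diary is due at three months, and 5.3.6 repeats retrieval at Day 90. The Day 30 wording is probably a slip, and that loss is not an expected effect.
- **Supply for all patients is tied to the Day 30 visit.** That holds only for isolated HIT.
- **Every Day 25 stop falls inside the period of raised thrombosis risk.** Section 5.1 counts that period from diagnosis, and 3.1.4 allows up to 7 days of another anticoagulant before enrollment. If diagnosis preceded the first dose by 7 days, Day 25 is 24 + 7 = 31 days after diagnosis.
- **Endpoint observation ends early.** The 5.3.7 contact covers the missing days, the HITT Day 90 visit covers discharge to Day 90, and 5.10 promises an effort to obtain Day 30 safety and survival information on early withdrawals. What remains is an isolated-HIT patient seen on Days 25 to 29 and then lost. The documents give no basis for estimating how many there would be.

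**Conclusion.** The point holds as a conflict between instructions. Sections 5.1 and 5.7 prescribe 30 or 90 days, while 5.3.5 and 5.3.6 permit a visit up to 5 days sooner and order drug retrieval whether or not dosing is complete. The largest effect is 5 of 30 days (10 of 60 doses, 17%) for isolated HIT and 5 of 90 days (6%) for HITT. It arises only where the visit is in person before the last scheduled day and drug is actually collected, or where supply was cut to an early visit. These figures count both doses on the visit day as taken.

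The inclusion of HITT patients in the Day 30 step is an error of wording to correct, not a loss to forecast. The gap in Day 30 status is small and largely closed by other contacts. The sample size and the success rule of 34 of 44 do not depend on this point. The correction is worth making because the instruction, followed as written, shortens treatment, and putting it right costs almost nothing.

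**What to change.** 1. In 5.3.5, 5.3.6 and the calendar, collect drug and diary only after the final scheduled dose: Day 30 for isolated HIT, Day 90 for HITT. State that a patient seen earlier keeps the drug.
2. Correct the calendar's Day 90 column heading to HITT.
3. In 5.3.4 and footnote 13, dispense for the full 30 or 90 days counted from first dose (74 or 194 tablets of 5 mg in total, including those given in hospital).
4. Confirm Day 30 status in one of two ways: open the visit window at Day 30 (Days 30 to 35), or keep the present window and telephone anyone seen on Days 25 to 29 on or after Day 30.

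Item 1 alone resolves the retrieval conflict; items 2 and 3 make the remaining text agree with it. No new success condition in 13.1 is needed.

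The cost is wording, plus either a 6-day window in place of 11 days or an occasional call, and 5.3.5 already accepts telephone follow-up. There are no additional patients or tests, and no drug beyond the planned course.
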